Total Radioactivity ^q (P2 Only)							X	→	→	→	→	→	→	→	→	→	X	→	→	X	→	→	X ^q				
Feces Sample collection for -																											
Total Radioactivity and Metabolite ID ^r (P1 Only)		X ^r	X	→	→	→	→	→	→	→	→	→	→	→	→	→	→	X	→	→	X	→	X	X	X	X ^r	X
[¹⁴ C]PF-06865571 ^r (P2 Only)							X ^r	→	→	→	→	→	→	→	→	→	→	→	→	→	→	X	→	→	X ^r		

Abbreviations: →= ongoing/continuous event; AE = adverse event; COVID-19 = Coronavirus disease 2019; CRU = Clinical Research Unit; ECG = electrocardiogram; ET=early termination; F/U=follow-up; HCVAb = hepatitis C antibody; HBsAg = hepatitis B surface antigen; HIV = human immunodeficiency virus; P1 = Period 1; P2 = Period 2; PK = pharmacokinetics; SAE = serious adverse event; LC/MS = liquid chromatography tandem mass spectrometry; ET = early termination.

Visit Identifier	Screening	Period 1 (P1) and Period 2 (P2), unless otherwise limited to 1 of these 2 Periods ^a																					F/U Phone Call	ET	
Days Relative to Day 1	-42 to -2	-1																							
Hours After Oral PF-06865571 Dose	-	-	0	0.5	1	2	3	3.08	3.17	3.25	3.5	3.75	4	6	9	12	16	24	27	36	48	51	72	96	120
Hours After IV [¹⁴ C]PF-06865571 Dose (P2 Only)			-3				0	0.08 3 (5 min)	0.17 (10 min)	0.25 (15 min)	0.5 (30 min)	0.75 (45 min)	1	3	6	9	13	21	24	33	45	48			

Note: Black color denotes oral dose administration and sampling post oral administration and Red color denotes IV dose administration and sampling post IV administration. IV samples may optionally be labeled with the corresponding time relative to the oral dose for sample collection; however, PK data for the IV administration will be analyzed relative to the start of the IV infusion.

- There will be a wash-out period of 8-22 days from drug administration in Period 1 and Period 2. The day to start Period 2 is dependent on the duration for Period 1 but will be at least after all sample collection in Period 1 are complete.
- In Period 2, participants will be discharged on Day 3 (ie, 48 hours IV dose administration).
- Dosing in Period 2 (as 1 cohort) or Completion of Period 1 (1 participant at a time) when at least 1 of 3 criteria are met: (1) ≥90% of radioactive dose has been recovered in urine+feces+emesis (if any); (2) <1% of radioactive dose has been recovered in urine+feces during 24H interval over 2 consecutive days; (3) participant has reached Day 21 (in Period 1). At the latest, Period 2, Day -1 would occur on the same day as Period 1, Day 21.

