4. STUDY DESIGN

4.1. Overall Design

This study is a Phase 1, open-label, non-randomized, 2-period, fixed-sequence, single-dose study of PF-06865571 in healthy male participants to characterize the ADME properties of [¹⁴C]PF-06865571 following oral administration; and to evaluate the absolute oral bioavailability (F) and fraction absorbed (Fa) of PF-06865571 following oral administration of unlabeled PF-06865571 and IV administration of [¹⁴C]PF-06865571.

In this study 6 participants will be enrolled to ensure evaluable data is acquired in at least 4 participants. Each participant will receive 2 regimens (A and B) in Periods 1 and 2, respectively, as outlined in Figure 1. Participants who withdraw from the study may be replaced if the number of evaluable participants is less than 4.

Figure 1. Two (2)-Period Fixed Sequence Study Design

* Completion of Period 1 (1 participant at a time) when at least 1 of 3 criteria are met: (1) $\geq 90\%$ of radioactive dose has been recovered in urine+feces+emesis (if any); (2) $< 1\%$ of radioactive dose has been recovered in urine+feces during 24H interval over 2 consecutive days; (3) participant has reached Day 21 (in Period 1). At the latest, Period 2, Day -1 would occur on the same day as Period 1, Day 21.

Regimen A in Period 1: An oral dose of 300 mg PF-06865571 containing approximately 300 nCi ^{14}C (ie, radiolabeled PF-06865571) will be administered within approximately 10 minutes of completion of a standard breakfast (see Sections 5.3.1 and 6.1.1).

Regimen B in Period 2: An oral dose of 300 mg unlabeled PF-06865571 followed at T_{max} by an IV dose of 300 nCi $[^{14}\text{C}]$ in 100 μg of PF-06865571 (3 $\mu\text{Ci}/\text{mg}$ active drug). The $[^{14}\text{C}]$ IV dose will be administered as an infusion over approximately 15 minutes. Oral unlabeled PF-06865571 will be administered within approximately 10 minutes of completion of a standard breakfast (see Sections 5.3.1 and 6.1.1).

Screening will occur within 42 days of the first dose of the investigational product in Period 1. All participants will provide informed consent and undergo screening evaluations to determine their eligibility.

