Eligible participants will be admitted to the CRU on Day -1 of Period 1 and scheduled to remain in the CRU through the completion of Period 2. As such, inpatient stay will be for a total duration of 12 days (minimum) to 25 days (maximum). Each participant will have 1 -follow-up phone call that will occur at least 28 days and up to 35 days following the last dose of investigational product to assess for AEs and SAEs.

In exceptional cases, participants may leave the CRU for personal reasons, at the discretion of the investigator, for up to a maximum of 8 hours during Period 1 after Day 7, if the participant has completed Period 1 based on the completion criteria defined in Figure 1.

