5.2. Exclusion Criteria

Participants are excluded from the study if any of the following criteria apply:

Medical Conditions:

1. Evidence or history of clinically significant hematological, renal, endocrine, pulmonary, gastrointestinal, cardiovascular, hepatic, psychiatric, neurological, or allergic disease (including drug allergies, but excluding untreated, asymptomatic, seasonal allergies at the time of dosing).
2. Any condition possibly affecting drug absorption (eg, gastrectomy, cholecystectomy).
3. History of irregular bowel movements including irritable bowel syndrome or frequent episodes of diarrhea or constipation, defined by less than 1 bowel movement on average per 2 days, or lactose intolerance.
4. History of HIV infection, hepatitis B, or hepatitis C; positive testing for HIV, HBsAg, or HCVA. Hepatitis B vaccination is allowed.
5. Other medical or psychiatric condition including recent (within the past year) or active suicidal ideation/behavior or laboratory abnormality or other conditions or situations related to the COVID-19 pandemic that may increase the risk of study participation or, in the investigator's judgment, make the participant inappropriate for the study.
 - History of SARS-CoV-2 PCR or antibody (eg, IgG, IgM, etc) positive result would necessitate accompanying history of asymptomatic state for at least 6 months prior to screening.

Prior/Concomitant Therapy:

6. Use of prescription or nonprescription drugs and dietary and herbal supplements within 7 days or 5 half-lives (whichever is longer) prior to the first dose of study intervention with the exception of moderate/potent CYP3A inducers which are

prohibited within 14 days plus 5 half-lives prior to the first dose of study intervention. (Refer to [Section 6.5](#) for additional details).

Prior/Concurrent Clinical Study Experience:

7. Previous administration with an investigational drug within 60 days (or as determined by the local requirement) preceding the first dose of study intervention used in this study (whichever is longer).

Diagnostic Assessments:

8. A positive urine drug test.
9. A positive urine cotinine test.
10. Screening supine BP ≥ 140 mm Hg (systolic) or ≥ 90 mm Hg (diastolic), following at least 5 minutes of supine rest. If BP is ≥ 140 mm Hg (systolic) or ≥ 90 mm Hg (diastolic), the BP should be repeated 2 more times and the average of the 3 BP values should be used to determine the participant's eligibility.

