 - This may include consumption of fiber capsules, at a frequency dictated by investigator, starting with the evening meal (ie, ~8H post dose) on Day 1, for duration of inpatient stay to ensure at least one bowel movement per day;
 - If an individual participant has not experienced a bowel movement in the first 24 hours after dosing, fluid intake should be increased and administration of a mild laxative [eg, prune juice or a mild stool softener (eg, docusate)] should be implemented, with the goal to facilitate at least one daily bowel movement;
 - Despite these measures, if bowel movement does not occur, on Day 2 and each subsequent day, consideration should be given to administration of mild laxative (eg, milk of magnesia), at the Investigator's discretion. The use of the stool softener / laxative needs to be recorded.

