9.3. Analysis Sets

For purposes of analysis, the following analysis sets are defined:

Participant Analysis Set	Description
Evaluable	All participants assigned to study intervention and who take at least 1 dose of study intervention.

Participant Analysis Set	Description
Extent of Excretion	Extent of excretion population is defined as all participants who have received 1 dose of [¹⁴ C]PF-06865571 and who have evaluable total radioactivity concentration (urinary and fecal) data and who had no protocol deviations or AEs (such as vomiting of the dose, diarrhoea or severe constipation) that may have affected the extent of excretion analysis.
PK Concentration	The PK concentration population for PF-06895571 is defined as all participants who receive at least 1 dose of PF-06895571 and who have at least 1 measurable concentration of PF-06895571. The PK concentration population for ¹⁴ C is defined as all participants dosed with [¹⁴ C]PF-06895571, who have at least one ¹⁴ C measurement.
PK Parameter	The PK parameter analysis population for PF-06895571 is defined as all participants treated who have at least 1 of the PF-06895571 PK parameters of interest. The PK parameter analysis population for ¹⁴ C analysis is defined as all participants treated who have at least one of the ¹⁴ C parameters of interest. The PK concentration and PK parameter analysis sets may differ.
Safety	All participants assigned to study intervention and who take at least 1 dose of study intervention. Participants will be analyzed according to the product they actually received.

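### The low-excretion stopping rule for Period 1 does not require a stool, so two stool-free days can end collection below 90% recovery

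*Protocol*

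**What the plan says.** The footnote to Protocol 1.3 (Schedule of Activities) and the footnote to Figure 1 in Protocol 4.1 give the same rule: "Completion of Period 1 (1 participant at a time) when at least 1 of 3 criteria are met". The criteria are at least 90% recovered in excreta; "<1% of radioactive dose has been recovered in urine+feces during 24H interval over 2 consecutive days"; or Day 21 reached. SAP 2.1 repeats the rule under its own Figure 1. None of the three places requires a stool in the qualifying intervals or says how an interval without one is scored.

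Other provisions bear on the risk:

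- **Eligibility (Protocol 5.2).** Irregular bowel habit is excluded, with the limit "defined by less than 1 bowel movement on average per 2 days". An average of exactly one movement per two days is not below that limit.
- **Bowel regimen (Protocol 5.3.1 and 6.5).** Fiber capsules may be used "for duration of inpatient stay to ensure at least one bowel movement per day". A mild laxative or stool softener is called for if there is no stool in the first 24 hours. Further laxative use is at the investigator's discretion.
- **Timing.** The variable part of Period 1 sits in the Day 7–21 column of the schedule (144–504 h). Protocol 4.1 permits short leave from the unit "after Day 7, if the participant has completed Period 1 based on the completion criteria defined in Figure 1". No section states a minimum day for criterion 2.
- **Analysis set (Protocol 9.3, SAP 5.2).** The Extent of Excretion set omits participants with deviations or adverse events that may have affected the analysis, such as "vomiting of the dose, diarrhoea or severe constipation".

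**The concern.** A low-excretion rule is meant to show that excretion has finished. Urine can show that day by day; feces can only do so when a stool is passed. Without a stool, the rule cannot tell finished from not yet voided. The criteria are alternatives, so nothing else in the rule catches the error.

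Total recovery in urine, feces and total excreta is a primary endpoint (Protocol 3). In a participant stopped this way, fecal and total recovery are truncated low and the split shifts toward urine. The error runs in one direction and cannot be repaired once collection has ended. With 6 participants enrolled and at least 4 evaluable required, one case shows in the summary. Fa is not affected, because it uses urine to 48 h only.

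**Working it through.** **No planned figure to reproduce.** The sample size is conventional and no hypothesis is tested (Protocol 9.1 and 9.2). The timeline does reproduce. Minimum stay: Day −1, then Days 1 to 9 (Period 2 dosing 8 days after Period 1 dosing), then 2 more days: 1 + 9 + 2 = 12. Maximum: 1 + 21 + 3 = 25. With dosing on Day 9, Period 2 Day −1 is Day 8, which begins at 168 h. So 168 h fits the minimum stay, while 144 h is where the variable column begins. Both were used as the first possible stop.

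**The rule as written.** Take 75% recovered, then two intervals with no stool and 0.5% in urine each. Cumulative recovery is 75 + 0.5 + 0.5 = 76%. Criterion 1 (at least 90%) is not met. Criterion 2 is met, since 0.5 < 1 twice. Period 1 is complete with 24% unrecovered. If all of that were still to be voided in one of 6 participants, mean recovery would be 24/6 = 4.0 points too low. In 15 such cases (40–88% already recovered, urine 0.1–0.9% per day) the written rule stops every time, at 40.2–89.8% recovery.

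**How often.** These inputs are not in the documents and are assumed:

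- stool gaps gamma distributed, mean 24, 36 or 48 h, CV 0.4;
- fecal label reaching the distal gut lognormally, median 40, 60 or 80 h, log-SD 0.5;
- 50% of excreted label in feces; urine first order with an 8 h half-life;
- eventual recovery 97%, or 88% (so criterion 1 can never be met);
- Day 21 cap at 480 h; 4,000 simulated participants per scenario.

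Two checks on these inputs. At 97% recovery, the urinary share is 48.5% of dose, and the 48–72 h interval yields 48.5 × (2^−6 − 2^−9) = 0.66%. Urine is therefore below 1% per day well before 144 h. The share of fecal label that has arrived by 144 h is Φ(ln(144/m)/0.5), which is 99.5%, 96% and 88% for m = 40, 60 and 80 h. Slow transit therefore drives the upper ends.

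Chance per participant of a stop on two stool-free days (range over the three transit times):

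| Mean stool gap | 97% recovery, from 144 h | 97% recovery, from 168 h | 88% recovery, from 144 h, losing at least 5 points |
|---|---|---|---|
| 24 h | 0–1.0% | 0–0.6% | 0–1.3% |
| 36 h | 0.3–14% | 0–8% | 0.5–17% |
| 48 h | 2–34% | 0.3–22% | 3–41% |

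At 88% recovery from 144 h, all such stops regardless of loss occur in 1.0–2.6%, 15–31% and 39–70%; many lose under 5 points.

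**Loss.** Compared with the same participant under the amended rule, an affected participant loses on average 8–14 points (97% case) or 1–9 points (88% case). One case in 6 lowers mean recovery by 1/6 ≈ 0.2 to 14/6 ≈ 2.3 points.

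**The case against.** The strongest reply is that this is an edge case the protocol largely controls.

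- At the protocol's own goal of a stool a day the risk is at most about 1%. The large figures come from 48 h gaps, which sit on the exclusion limit, and the simulation has no response to fiber or laxatives.
- The 8-day dose interval and 12-day minimum stay fit a 168 h start better than 144 h. From 168 h with 88% recovery, stops losing at least 5 points fall to about 0–10% at 36 h gaps and 0.5–30% at 48 h.
- The fecal fraction is a single assumed value. With 20% in feces, 97% recovery and a 168 h start, the chances are 0%, 0–0.3% and 0–3.3% at 24, 36 and 48 h gaps.
- Recovery is reported by interval with individual cumulative curves (Protocol 9.4.1.1, SAP 8.2.1), so a flat, stool-free tail would be seen. The Extent of Excretion set also requires evaluable fecal data, and severe constipation is only an example of what removes a participant.

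All of this stands as a limit on size. It does not change the rule. The regimen is a goal with discretionary escalation and is not tied to criterion 2. Severe constipation is undefined, and a two-day gap need not be reported as such. Seeing the truncation afterwards does not recover the sample, and removing the participant costs one of 6.

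**Conclusion.** The concern holds. As written, criterion 2 can complete Period 1 on two stool-free days with low urine output at any recovery below 90%. That follows from the wording alone and needs no assumption. How often it would happen, and whether label would in fact remain in the gut, cannot be settled from the documents. On the assumed inputs the risk is negligible with near-daily stools and becomes material only at mean gaps of about 36–48 h, mostly with slow transit and a substantial fecal fraction. The consequence is a one-sided loss in a primary endpoint, of the order of 1–14 points in the affected participant and 0.2–2.3 points in a mean of 6. This is a change that should be made because it is cheap and the loss is irreversible; it is not a fatal flaw. Confidence in the size is medium.

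**What to change.** Add one clause to criterion 2 in the Schedule of Activities footnote, the Protocol Figure 1 footnote and the SAP Figure 1 footnote: *at least one fecal sample must have been collected and assayed within the two consecutive 24H intervals; two stool-free intervals alone do not meet the criterion*. Criteria 1 and 3, including the Day 21 cap, stay as they are.

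In the simulation this removed every two-stool-free-day stop in all 36 scenarios. Mean Period 1 lengthened by 0–0.4 days at 97% recovery and 0–3.0 days at 88% (longest at 48 h gaps). Affected participants stayed about 1 day longer (97%) or 2–4 days longer (88%), and none of them reached the cap. Period 2 is dosed as one cohort, so the cohort may wait that long within the existing maximum.

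Requiring a stool in both intervals is not recommended. At 48 h gaps, 88% recovery and a 144 h start it added 6–7 days on average and sent 16–28% of participants to Day 21.

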2. INTRODUCTION

PF-06865571 is a diacylglycerol acyltransferase 2 (DGAT2) inhibitor that is currently being developed for the treatment of nonalcoholic steatohepatitis (NASH) with liver fibrosis.

2.1. Study Rationale

The purpose of this study is to assess the extent of excretion of PF-06865571 as well as the absolute bioavailability, fraction absorbed and pharmacokinetics of PF-06865571 in healthy male participants using a ¹⁴C microtracer dose approach.

2.2. Background

Diacylglycerol acyltransferases (DGATs) catalyze the terminal step in triglyceride (TG) synthesis; specifically, the esterification of a fatty acid with diacylglycerol (DAG) resulting in the formation of TG.¹ In mammals, two structurally unrelated DGAT enzymes (DGAT1 and DGAT2) have been characterized. DGAT1 is highly expressed in the intestine and plays a central role in fat absorption.² DGAT2 is highly expressed in liver and adipose.³ In preclinical models, blockade of hepatic DGAT2 using antisense oligonucleotides results in both down-regulation of the expression of multiple genes encoding proteins involved in lipogenesis and parallel induction in oxidative pathways.^{4,5} The net result of these changes is a decrease in the levels of hepatic DAG and TG lipid which, in turn, reduces hepatocyte lipid burden and decreases hepatic very low density lipoprotein (VLDL) TG secretion.^{5,6} PF-06865571 is a potent, reversible oral, small molecule DGAT2 inhibitor that is postulated to decrease hepatic TG synthesis and hepatic lipid burden in non-alcoholic fatty liver disease (NAFLD) and nonalcoholic steatohepatitis (NASH). Based on observations in nonclinical studies conducted, it is hypothesized that DGAT2i will impact both physiological drivers contributing to NASH via direct inhibition of liver triglyceride synthesis, as well as adaptive responses leading to reduction in hepatic DNL. Following 2 weeks of dosing in participants with NAFLD, DGAT2i has been shown to reduce liver fat in a dose-responsive manner.

2.2.1. Nonclinical Pharmacokinetics and Metabolism

Nonclinical studies indicate that PF-06865571 was rapidly absorbed in rat and moderately absorbed in monkey with mean oral bioavailability of 31% and 48%, respectively. In vitro, PF-06865571 showed high passive permeability, and preliminary studies indicated that PF-06865571 was a substrate for multi-drug resistance protein (MDR)1 (also known as P-glycoprotein [P-gp]) and mouse breast cancer resistance protein (mBCRP) efflux transporters.

PF-06865571 was moderately bound to plasma proteins. The mean unbound fraction of PF-06865571 was 0.464, 0.213, 0.331, 0.419, 0.360, and 0.353 in rat, rabbit, dog, monkey, and human plasma, respectively, with PF-06865571 preferentially distributing into plasma relative to blood.

The major primary metabolic pathway identified from preliminary in vitro and in vivo metabolite profiling in human is O-de-ethylation with subsequent sulfation and glucuronidation. There was no evidence of human unique metabolites. Reaction phenotyping studies indicate the total cytochrome P450 (CYP) contribution to PF-06865571 metabolism was >96%, and CYP3A was the predominant isoform responsible for the metabolism of PF-06865571 suggesting a risk of clinical drug-drug interactions (DDI) with PF-06865571 as a victim upon co-administration with CYP3A inhibitors or inducers.

While in vitro data suggest that PF-06865571 has the potential to induce CYP3A4 and CYP2B6, in a clinical study (C2541002), there was no dose-response relationship of endogenous biomarkers of CYP3A4 induction with increasing repeated doses of PF-06865571 up to 1800 mg/day. PF-06865571 also has the potential to inhibit uridine diphosphate-glucuronosyltransferase (UGT) 1A1, UGT1A9, and UGT2B15 based on in vitro data from human liver microsomes. In addition, in vitro evaluations suggest that PF-06865571 has the potential to inhibit CYP2C9, intestinal CYP3A, P-gp, breast cancer resistance protein (BCRP), organic cation transporter (OCT)1, OCT2, and multidrug and toxic compound extrusion transporter (MATE)1 at the highest planned clinical dose in the program going forward (ie, 300 mg twice daily [BID]).

2.2.2. Clinical Overview

2.2.2.1. Summary of Clinical Safety

As of the issuance of this protocol, 9 clinical studies with PF-06865571 have been completed. Across these 9 studies, a total of 306 unique participants have been randomized. This includes 141 unique healthy adult participants, 18 adults with hepatic impairment, and 165 adults with NAFLD. Of the 306 participants randomized, 231 (75%) were exposed to PF-06865571 - 65 unique participants (28%) to single oral doses of PF 06865571 and an additional 166 participants (72%) to repeated, oral, doses of PF-06865571 for up to 6 weeks.

Administration of PF-06865571 alone has been found to be well tolerated with the maximum tolerated dose not identified and no adverse drug reactions identified. Upon administration of single oral doses of PF-06865571, across the 300-fold dose range evaluated (ie, 5 to 1500 mg), TEAEs reported in ≥ 4 participants across all arms evaluated were headache (12%), and diarrhea (7%).

2.2.2.2. Summary of Clinical Pharmacology

Following administration of single oral doses of PF-06865571 under fed conditions in C2541001, median time for C_{max} (T_{max}) ranged from 1.5 to 4 hours across the dose groups. Approximate dose-proportional increases in C_{max} and AUC_{24} were observed between the 5 mg and 1500 mg doses. Under fed conditions, the mean terminal elimination half-life ($t_{1/2}$) ranged from 1.5 to 5.2 hours. At the 1000 mg dose level, exposures under fasted condition were approximately 2-fold lower than those in the fed state. Median PF-06865571 T_{max} occurred earlier in the fasted state, compared to dosing under fed conditions (1 h versus 4 h). In addition, the terminal elimination $t_{1/2}$ under fasted conditions was more variable than under fed conditions.

Following repeated administration of oral doses of PF-06865571 under fed conditions in C2541002, C_{max} values on Days 1, 7 and 14 were observed within a median T_{max} range of 1.5 to 3.0 hours post-dose across the 30 mg - 600 mg Q8H doses. Steady state appeared to have been reached by Day 4 based on PF-06865571 median trough plasma concentration-time profiles. Following a single dose on Day 1 and at steady state (Days 7 and 14), PF-06865571 plasma exposure across the 30 mg - 600 mg Q8H doses appeared to increase in a dose proportional manner based on geometric mean AUC_{tau} and C_{max} values. Mean $t_{1/2}$ on Day 14 ranged from 3.29 hours to 6.92 hours across the 30 mg - 600 mg Q8H doses with longer $t_{1/2}$ values observed at higher doses. Minimum drug accumulation was observed following multiple dose administration of PF-06865571 Q8H. Mean accumulation ratios ranged from 0.950 to 1.33 based on AUC_{tau} values and 0.990 to 1.44 based on C_{max} values across all doses on both Day 7 and Day 14. The proportion of drug excreted via renal elimination on Day 14 was low, with less than approximately 2% (mean $Ae_{tau}\%$ values ranged between 0.696% and 1.79%) of the dose excreted in urine as unchanged drug over the dosing interval across the 30 mg - 600 mg Q8H doses. Mean CL_r values ranged between 0.293 to 0.630 L/hr.

